5.2 Primary Safety Endpoints

The primary safety endpoint is defined as the incidence of Major Complications, as defined below:

Major Complications during the procedure through 7 days:

- Death
- Stroke
- Myocardial Infarction
- Diaphragmatic paralysis
- Transient Ischemic Attack (TIA)
- Cardiac Tamponade
- Pericarditis
- Pneumothorax
- Hospitalization or Emergency Room Visit
- Vascular Access Complication
- Heart Block
- Pulmonary Edema
- Pericardial Effusion resulting in pericardiocentesis or surgical intervention
- Thromboembolism

Major Complications during the procedure through 180 days:

- Pulmonary vein stenosis
- Atrio-esophageal fistula

Major Complication definitions can be found in **Appendix L** of this protocol. All Major Complications, as reported by the clinical investigator, will be reviewed and adjudicated by the Clinical Events Committee (CEC).

All adverse events will be documented and collected once the informed consent has been signed.

In the event of a study subject death, all possible efforts will be made to obtain relevant records from the hospital or the subject's primary care physician, including death certificates, to determine the cause of death.

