5.3 Primary Effectiveness Endpoint

The primary effectiveness endpoint is chronic success. Chronic success is defined to be:

- Freedom from symptomatic atrial fibrillation, atrial flutter, and atrial tachycardia episodes from days 91 - 365 after the initial ablation procedure, as documented by event recording, ECGs, and Holter monitoring.
- No use of Class I, Class II, Class III or Class IV antiarrhythmic medications during days 91 - 365 after the initial ablation procedure with the following exceptions.
 - Addition of Anti- Arrhythmic (AAD) medication which was previously ineffective for AF and does not exceed the previous historical maximum dosage (24 hour total dose).
 - Use of Atrioventricular (AV) nodal blocking agents such as beta blockers (BB) and/or calcium channel blockers (CCB) that are maintained at the current dose (does not exceed previous historical maximum dosage (24 hour total dose).
- No more than two additional ablation procedures within 90 days of the initial ablation procedure and no additional ablation procedures after day 90.
- No use of a non-study device for ablation of any atrial fibrillation target. Commercially available non-study devices may be used for atrial flutter and atrial tachycardia ablation targets.
- No ablation of an atrial fibrillation target made by removing the ablation catheter from the Artisan catheter and manually manipulating the ablation catheter.
- Pulmonary vein isolation of at least 3 out of 4 veins confirmed by pulmonary vein entrance block during the last procedure within the blanking period.
- No surgical ablation for atrial fibrillation, atrial flutter, or atrial tachycardia within 90 days of the initial ablation.
- No direct current (DC) cardioversion for atrial fibrillation, atrial flutter, or atrial tachycardia within days 91 - 365 after the initial ablation procedure.
- No catheter or surgical ablation for atrial fibrillation, atrial flutter, or atrial tachycardia within days 91 - 365 after the initial ablation procedure.

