5.4 Secondary Endpoints

- **Acute Procedural Success**

Acute procedural success is defined as the successful ablation of at least three of four pulmonary veins as shown by pulmonary vein entrance block per vein during the initial ablation procedure. A subject is considered to be an acute procedural failure if acute procedural success cannot be obtained by using the Hansen system and, as a result, manual manipulation is needed to complete the ablation procedure with the ablation catheter.

- **Chronic Safety**

Chronic safety is defined as the incidence of Major Complications during the period from 8 – 365 days following the initial ablation procedure (excluding pulmonary vein stenosis and atrio-esophageal fistula from 8 – 180 days, which are included in the

primary safety endpoint). The incidence of pulmonary vein stenosis and atrio-esophageal fistula is included during the period from 181 – 365 days.

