6.0 Statistical Hypotheses

6.1 Primary Safety Endpoint

The primary safety endpoint is defined as the incidence of Major Complications, including all early onset (within 7 days of the ablation procedure) Major Complications, and the incidence of esophageal injury or pulmonary vein stenosis through 180 days. The study is designed to determine if the Major Complication rate meets the pre-established target performance goal (TPG) of 16%. The null hypothesis and alternative hypothesis are:

$H_0: \pi_s \geq 16\%$ vs. $H_1: \pi_s < 16\%$,

where π_s is the probability of having a primary safety event. The null hypothesis is rejected when at least 95% of the posterior distribution below 16%.

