6.3 Secondary Safety Endpoint – Chronic Safety

The secondary safety endpoint is demonstration of the long term safety of remotely introducing and positioning ablation catheter through the Artisan Guide Catheter. The secondary safety endpoint is defined as the incidence of Major Complications from days 8 to 365.

The proportion and the one-sided 95% upper confidence level will be calculated for long term safety using the Kaplan-Meier method to account for censoring. No hypothesis test will be performed for the secondary safety endpoint.

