- Low molecular weight or intravenous heparin should be used as a bridge to resumption of systemic anticoagulation following catheter ablation and sheath removal. All subjects should be on anticoagulation therapy for at least two months following the procedure. Decisions regarding the use of anticoagulation therapy for longer than two months following procedure should be based on the subject's risk factors for stroke and not the presence or type of AF. A CHADS₂ score will be used to determine the risk of stroke for the subjects and their need for anticoagulation therapy. Discontinuation of anticoagulation therapy beyond two months post ablation is not recommended in subjects who have a congestive heart failure, history of high blood pressure, age (75 years), diabetes, prior stroke or transient ischemic attack CHADS₂ score of ≥ 2 . Either aspirin or warfarin is appropriate for subjects with a CHADS₂ score of 1. Refer to **Appendix N** for the CHADS₂ score.

This anticoagulation strategy is based on the 2012 HRS Consensus Task Force recommendations, as listed on Table 4, Page 24 of the referenced HRS document.

- Each subject may be treated again using the Hansen System up to two more times during the blanking period.

- Any follow-up ablation procedure conducted within the study timeline for each patient, will need to be documented. The repeat ablation procedural date(s) and if the procedure was conducted manually or robotically will be the data points collected in the study database.
- Proton pump inhibitors should be administered for 4 weeks post ablation.

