7.8.3 Major Complications

Major Complications are adverse events which may occur in conjunction with or following atrial ablation that are included in the primary safety endpoint for this study. The list and definitions for adverse events that are considered Major Complications are outlined in **Appendix L**.

Should a Major Complication occur, the investigator is required to report by eCRF all available information regarding the Major Complication to the Sponsor promptly upon learning of the event. Additional time may be required in order to obtain the background details related to a Major Complication; however, the report of its occurrence should be made to the Sponsor once the investigator first learns of the event. All related medical records will be required for submission to Hansen Medical for Major Complications that are reported.

All potential Major Complications reported will be reviewed and adjudicated by the CEC. Major Complications will be classified as either a Primary Safety Endpoint or a Chronic Safety Event depending on the event occurrence following the ablation procedure, (Refer to definitions in Sections 5.2 and 5.4).

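### Acute complications of a repeat study-device ablation after day 7 go to the untested chronic safety endpoint, or meet both safety definitions, while tested effectiveness credits the repeat

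*Protocol*

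**What the plan says.** **Repeats.** Protocol section 7.3.3 (post-procedural care): "Each subject may be treated again using the Hansen System up to two more times during the blanking period". Section 5.3 makes this compatible with chronic success, the condition being "No more than two additional ablation procedures within 90 days of the initial ablation procedure". The same section judges vein isolation at the last blanking-period procedure, so a repeat can supply it.

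**Primary safety.** Section 5.2 lists "Major Complications during the procedure through 7 days", and section 6.1 describes the endpoint as "including all early onset (within 7 days of the ablation procedure) Major Complications". The synopsis and section 7.7 use similar words. None of them says whether the initial ablation or any ablation is meant. Stenosis and fistula are counted to day 180. The endpoint is tested against 16%.

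**Chronic safety.** Section 5.4 names its anchor: "Chronic safety is defined as the incidence of Major Complications during the period from 8 – 365 days following the initial ablation procedure". Its one exception for events that belong to the primary endpoint is worded "excluding pulmonary vein stenosis and atrio-esophageal fistula from 8 – 180 days". Section 6.3 adds: "No hypothesis test will be performed for the secondary safety endpoint".

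**Classification.** Section 7.8.3: "Major Complications will be classified as either a Primary Safety Endpoint or a Chronic Safety Event", according to when the event occurs and with reference to sections 5.2 and 5.4.

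**Follow-up.** Section 5.1 counts the 7-day contact from the initial ablation. For repeats, section 7.3.3 names only the date and whether the procedure was manual or robotic as data points.

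**The concern.** The treatment under study is a course of one to three procedures, and study success requires both co-primary tests to pass. Effectiveness is credited to the whole course; single-procedure success is only an untested additional analysis. If the 7-day safety component follows section 5.4, a tamponade, stroke or vascular access complication during a robotic repeat on day 60 is a late event that no test sees, although it is an acute complication of the device being evaluated. The tested complication rate is then lower than the rate for the treatment whose benefit is tested. The chronic endpoint, meant to describe late events, also picks up peri-procedural ones.

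**Working it through.** **1. The text, for a tamponade during a robotic repeat on day 60.**
- Section 5.4: day 60 after the initial ablation lies within days 8-365, and tamponade is not in the exception. It is a chronic event.
- Sections 5.2, 6.1 and 7.7: if the unnamed procedure is the initial one, the event is outside the primary endpoint, in agreement with 5.4. If it is any ablation, the event is inside the primary endpoint and inside 5.4 as well.
- Section 7.8.3 allows only one class. The first reading puts the event outside the test; the second leaves a contradiction for the Clinical Events Committee to settle.

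**2. The plan's own figure.** Section 6.5 states 98% probability of success at true rates of 8% (safety) and 72% (effectiveness). Sections 6.1 and 6.2 require at least 95% posterior probability below 16% and above 54%. The prior is in Appendix M, which is not shown, so Beta(1,1) is assumed, with independent endpoints and a final analysis only.
- N=250: pass with at most 30 safety events and at least 148 successes; joint probability 0.990.
- N=238 (250 less the 5% expected pre-procedure withdrawals): at most 28 and at least 142; 0.984.
- N=125: at most 13 and at least 77; 0.870.
- A simplified adaptive simulation (1,500 runs; accrual and a 5% futility cut-off assumed) gave 0.983 at 5 subjects per month and 0.955 at 10 per month.

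The stated 98% is approximately reproduced, so the simplified rule is adequate for judging size.

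**3. Counting the repeats.** Let p be the rate at the first procedure and r the share of subjects with one repeat, after day 7, at the same risk. The per-subject rate is p + r·p·(1-p). For example, 0.08 + 0.20 × 0.08 × 0.92 = 0.0947. The protocol gives no r; 10-30% is assumed. The chance of passing safety is the binomial probability of at most 30 of 250, or 13 of 125.

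| p | r | Per-subject rate | Pass, N=250 | Pass, N=125 |
|---|---|---|---|---|
| 8% (section 6.5) | 0 | 8.0% | 0.990 | 0.874 |
| | 10% | 8.7% | 0.969 | 0.798 |
| | 20% | 9.5% | 0.926 | 0.705 |
| | 30% | 10.2% | 0.851 | 0.601 |
| 11% (reference study, section 6.6) | 0 | 11.0% | 0.733 | 0.486 |
| | 10% | 12.0% | 0.553 | 0.353 |
| | 20% | 13.0% | 0.368 | 0.241 |
| | 30% | 13.9% | 0.216 | 0.155 |

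The displaced events number 250 × r × p: 2 to 6 at p = 8%, against a limit of 30.

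**4. If the 16% is meant to bound the whole course.** Setting p + r·p·(1-p) = 0.16 gives p = 14.7%, 13.6% and 12.7% for r = 10%, 20% and 30%. An endpoint limited to the first procedure then passes at N=250 with probability 0.13, 0.26 and 0.42, against 0.047 when the counted rate is itself 16%.

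**5. Limits of the arithmetic.** Using the full p for repeats overstates the displacement to the extent that p contains stenosis and fistula, which already count to day 180. Second repeats, ignored here, work the other way.

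**The case against.** The best counter-argument is that the primary endpoint never says initial. The protocol writes that word where it means it, repeatedly in section 5.3 and again in 5.4, so its absence from 5.2, 6.1, 7.7 and the end of the 7.8.3 sentence may mean any ablation. This stands in part: the primary text alone does not settle the anchor, and Appendix L, not shown, might. It does not remove the problem. Section 5.4 lifts only stenosis and fistula out of days 8-365, which implies that other events after day 7 are not primary, and the looser reading places the same event under both definitions.

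Two stronger inferences are tempting and are not supported. A reader might conclude that tested safety carries the acute risk of the first procedure only. It does not: stenosis and fistula after a repeat count to day 180, and so does any listed complication of a repeat that falls within days 0-7. A reader might also conclude that the test is biased against its goal by the amounts shown. Section 6.6 builds 16% as 11% plus a 5-point margin and calls the two studies' endpoints equivalent, but it does not say whether the 11% included complications of repeats. If it did not, counting them here against an unchanged 16% would create a mismatch of its own.

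Nor are the events lost. They are reported, adjudicated, open to the Data and Safety Monitoring Board, and included in a Kaplan-Meier estimate with a one-sided 95% upper limit. What they lack is a place in the pass/fail count.

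**Conclusion.** The point holds in this form. Section 5.4, read with section 7.8.3, sends acute Major Complications of a blanking-period repeat after day 7, other than stenosis and fistula, to an endpoint without a test; on the looser reading of 5.2 and 6.1 the definitions overlap. Either way the co-primary safety count depends on an anchor that the sections do not state consistently, while effectiveness credits up to two repeats. The direction is fixed by the text: leaving the events out can only lower the tested rate, which favours the device. The size is not fixed. It is modest at the 8% planning rate and large at 11%, and rests on an assumed repeat share of 10-30%, one repeat each, equal risk per procedure, a flat prior and a single final analysis. Whether the 16% goal itself is misapplied cannot be decided from the protocol.

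**What to change.** - In the synopsis and sections 5.2, 6.1 and 7.7, define the 7-day component as any listed Major Complication from the start of, through 7 days after, the initial or any repeat study-device ablation in the blanking period, counted once per subject. Leave the day-180 stenosis and fistula component as it is.
- In sections 5.4 and 6.3, exclude those events from chronic safety, so that the rule in 7.8.3 gives one answer. Check Appendix L for the same anchor.
- Make the 7-day safety assessment apply after each repeat as well as after the initial ablation.
- In section 6.6, state whether the 11% reference rate counted complications of repeat procedures, so that the 16% goal is read on the same basis. Report the index-procedure-only rate as a sensitivity analysis.

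The data burden is small, since adverse events and repeat dates are already collected; one contact per repeat is added. The real costs are a slightly less favourable observed rate and an amendment to a primary endpoint during enrolment (Table 6 shows 74 subjects in the single-arm study), which section 13.3 routes through the FDA and the ethics boards. The safety imputation model in Appendix M should be checked against the new definition.

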5.5 Additional Analyses

- Length of hospital stay,
- Total ablation time,
- Total ablation energy,
- Total fluoroscopy time,
- Total procedure time (defined as the duration of time from obtaining vascular access to sheath removal),
- Non-AF targets ablated manually,
- Ablative lesion sets in addition to those required for pulmonary vein isolation,
- Adverse events,
- Serious Adverse Events,
- Chronic success rates for subjects treated with a single procedure.

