5.0 Study Design

This is a prospective, single-arm, multi-center, US and OUS study to evaluate the safety and effectiveness of the family of Artisan guide catheters with the Sensei[®] X Robotic Catheter System for introducing and positioning one of a set of specified commercially available ablation catheter in subjects with paroxysmal atrial fibrillation. Up to 14 investigational sites will participate in this study to enroll a minimum of 125 and up to a maximum of 250 subjects.

Interim analyses will be conducted starting after the first 125 subjects are enrolled, and continuing every 25 subjects thereafter. At each interim analysis, enrollment may be stopped for expected success or for futility. If there is at least 95% probability that both the safety and effectiveness analysis will meet the success criteria if enrollment stops at the current sample size and all patients are followed to the 12-month endpoint, then enrollment will stop early for expected success. Up to three additional interim analyses will be performed: after full enrollment and at 3 and 6 months after full enrollment to assess the criteria for an early declaration of success. If there is at least 99.9% probability that both the safety and effectiveness analyses will meet the success criteria after all enrolled subjects are followed to the 12-month endpoint, and if a minimum of 80 and 100 patients have complete follow-up for the effectiveness and safety endpoints, respectively, then the trial will declare early success. A clinical study report can then be prepared for submission to the FDA.

Subsequently, the final analysis will occur when the 12-month follow-up is complete for all enrolled subjects. An updated final clinical study report will then be prepared and submitted to the FDA to close out the IDE study.

Based on the interim analyses defined for the study, the maximum number of subjects allowed at any site at each interim analysis is defined in the following table.

Table 7: Maximum Subjects per Site at Each Interim Analysis

Interim Analysis Sample Size	Maximum Subjects per Site
125	25
150	30
175	35
200	40
225	45
250	50

Study subjects with symptomatic, drug-refractory paroxysmal atrial fibrillation will undergo a catheter-based ablation procedure as part of this study to eradicate the aberrant atrial rhythm. If necessary, up to two additional catheter ablation procedures within the 90-day blanking period following the initial ablation procedure may be performed.

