6.7 Data Analysis

All statistical analyses will be done using the SAS software version 9.3 or later (Copyright © 2000 SAS Institute Inc., [name], USA. All rights reserved), R software or StatXact (Copyright © 2010, 1989-2012, Cytel Software Corporation).

All data will be collected as detailed in the clinical trial schedule. Subject demographics, medical history, risk factors, procedure characteristics, and outcome variables will be summarized using descriptive statistics for continuous variables (e.g. mean, standard deviation) and frequency tables or proportions for discrete variables.

The “Intention to Treat” (ITT) population includes all enrolled subjects. This includes subjects who signed an informed consent form. Subjects who are not enrolled due to not meeting the intra-procedural criteria are considered to be withdrawn from the study. Subjects who have already had a 14F introducer sheath introduced who subsequently are withdrawn during the procedure prior to treatment with the study device will be monitored for any acute adverse events related to the introduction of the 14F introducer sheath. Acute safety data for these subjects will be reported as a separate cohort, since these subjects are not treated with the study device. Additional subjects may be enrolled to replace subjects who were withdrawn due to not meeting the intra-procedural enrollment criteria. The primary statistical analysis will be performed on the cohort of subjects who are enrolled, meet the intra-procedural enrollment criteria, and are treated with the study device.

The following additional endpoints will be analyzed but will not be tested for statistical significance and will be reported as proportions, or means and standard deviations.

- Length of hospital stay,
- Total ablation time,
- Total ablation energy,
- Total fluoroscopy time,
- Total procedure time,
- Non-AF targets ablated manually,
- Ablative lesion sets in addition to those required for pulmonary vein isolation,

- Adverse events,
- Serious Adverse Events,
- Chronic success rates for subjects with a single procedure.

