7.3.4 Antiarrhythmic Drug (AAD) Therapy

If the subject is being maintained on beta blocking agents, calcium channel blockers or digitalis for a condition other than for AAD purposes, this medication shall be maintained throughout the duration of the subject's involvement in this investigation unless deemed unnecessary or detrimental to the subject by the treating physician.

- Procedure through 90 days (blinking period)

After the ablation procedure, subjects may be placed on AAD therapy:

- As prophylaxis for early AF recurrence
- For treatment of left atrial flutter

A new medication or a previously prescribed medication may be used.

It is recommended to withdraw AAD therapy 4-6 week post procedure to evaluate the subject's arrhythmia status.

- If symptomatic AF recurs following removal of AAD therapy during the blinking period, subjects may be offered an additional ablation procedure and/or placed on long term AAD therapy at the discretion of the investigator with a previously ineffective, but tolerated AAD dose.
- Class I, Class II, Class III and Class IV drugs may be used except amiodarone
- It is recommended that subjects be started on long term AAD therapy no later than 1-2 weeks prior to the end of the blinking period to ensure that adequate dosing is achieved.
- 91 - 365 days (after the blinking period)
 - Subjects may continue or start a previously used AAD medication up to the maximum historical dose 2 years prior to the procedure

As a component of the primary effectiveness endpoint, success with respect to AAD therapy is defined as:

- Freedom from AAD therapy from 90-365 days (after the blinking period)
- Use of previously used AAD medication from 90-365 days which does not exceed the maximum historical dose 2 years prior to the procedure

An AAD failure is defined as:

- Use of previously used AAD medication from 90-365 days (after the blanking period) which exceeds the maximum historical dose 2 years prior to the procedure
- New AAD therapy (not previously taken prior to procedure or during the blanking period) started after the blanking period

This antiarrhythmic treatment strategy is based on the NaviStar® ThermoCool® IDE study. The strategy acknowledges that it is common practice to reinstitute antiarrhythmic drug therapy to attempt to control the AF.

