8.3 Potential Benefits

Although there is no guarantee of benefit, the Hansen System may offer the following benefits to the delivery of the ablation catheter with the intent to isolate and treat the pulmonary veins

- Effective single treatment success rate,
- Reduced procedure time,
- Reduced exposure time to ionizing radiation for the subject and physician.

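### The planned single-procedure success rate leaves re-ablated subjects out of its denominator, so it overstates single-procedure success among all treated subjects

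*Protocol*

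**What the plan says.** Protocol section 5.5 lists, among its additional analyses, "Chronic success rates for subjects treated with a single procedure". Section 6.7 repeats the item as "Chronic success rates for subjects with a single procedure" and says of the whole list that it "will be analyzed but will not be tested for statistical significance". Neither section gives a wider denominator or says how a repeat ablation counts for this item.

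Repeats are part of the design. Section 5.0 states: "If necessary, up to two additional catheter ablation procedures within the 90-day blanking period following the initial ablation procedure may be performed". Section 7.3.4 names the usual trigger: "If symptomatic AF recurs following removal of AAD therapy during the blinking period, subjects may be offered an additional ablation procedure", with drug therapy as an alternative or an addition, at the investigator's discretion. The blanking-period definition in section 15.0 likewise permits re-treatment of a subject who stays symptomatic.

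The primary effectiveness endpoint in section 5.3 requires "No more than two additional ablation procedures within 90 days of the initial ablation procedure and no additional ablation procedures after day 90". Its cohort, in section 6.7, is the subjects who "are enrolled, meet the intra-procedural enrollment criteria, and are treated with the study device".

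**The concern.** A single-procedure rate is normally read as the chance that one ablation is enough for a patient who starts treatment. The group named in sections 5.5 and 6.7 is formed later, by what happened after the first ablation. A repeat is typically prompted by early recurrence, so subjects for whom one procedure did not suffice tend to be removed, not counted against it. Taken literally, the wording also removes subjects re-ablated after day 90, who are failures on the primary endpoint.

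The primary endpoint does not fill the gap, because a subject re-ablated once or twice by day 90 can still be a chronic success. The line in section 5.5 is therefore the only planned figure on single-procedure effectiveness, and it answers a conditional question. At stake is how a descriptive result will be read; the test of the device is untouched.

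**Working it through.** The protocol states neither a single-procedure rate nor an expected repeat rate, so there is no planned figure to reproduce.

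**Notation.** N = subjects in the primary analysis cohort. R = those with at least one repeat ablation, r = R/N. S1 = chronic successes who had one procedure only.

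**Two rates.**
- As listed in 5.5 and 6.7: S1/(N − R).
- Over all treated, repeat counted as failure: S1/N.
- Ratio of the first to the second: N/(N − R) = 1/(1 − r), above 1 whenever R > 0 and S1 > 0.

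The direction follows from the wording alone; the size depends on r, which is assumed below.

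**Hypothetical all-treated rate of 54%.** This number is borrowed for illustration from the performance goal, which belongs to an endpoint that allows repeats.

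| r (assumed) | Listed rate = 0.54/(1 − r) | Overstatement |
|---|---|---|
| 5% | 0.54/0.95 = 56.8% | 2.8 points |
| 10% | 0.54/0.90 = 60.0% | 6.0 points |
| 20% | 0.54/0.80 = 67.5% | 13.5 points |

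**The other direction.** Suppose the listed rate came out at 72%, the primary effectiveness rate assumed in section 6.5 (again only an illustration). The all-treated rate is 0.72 × (1 − r): 68.4% at r = 5%, 64.8% at 10%, 57.6% at 20%. In counts, with N = 250 (the maximum in section 6.5) and 50 subjects re-ablated, 144 successes among the other 200 give 144/200 = 72.0% as listed and 144/250 = 57.6% of all treated.

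**Comparison with overall chronic success.** Let the overall rate be 72%, r = 20%, and let q be the success rate among re-ablated subjects (assumed). The listed rate is (0.72 − 0.20q)/0.80.
- q = 50%: (0.72 − 0.10)/0.80 = 77.5%, above the overall rate; all-treated single-procedure rate 0.775 × 0.80 = 62%.
- q = 80%: (0.72 − 0.16)/0.80 = 70.0%, below the overall rate; all-treated single-procedure rate 0.70 × 0.80 = 56%.

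The listed rate can thus fall on either side of overall chronic success, but is above the all-treated single-procedure rate in both cases.

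**The case against.** The strongest reply is that the item is one line in a descriptive list and is honestly worded: it promises a rate for subjects who had a single procedure, and a conditional rate labelled as such is not false. An analysis plan that is not shown might also set the denominator differently. Part of this stands. The subset rate is a legitimate quantity if presented as conditional. But the protocol names the subset twice and offers no all-treated figure beside it, so as written the more useful number is absent. The protocol already uses the other logic for acute success (sections 5.4 and 6.4), where a subject who needs manual manipulation because the system did not achieve isolation is counted as a failure and kept in.

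Three stronger readings are tempting, and the document does not support them.
- *The subset is those who needed only one procedure, so all early failures are gone.* Section 7.3.4 lets early recurrence be handled with drugs instead of a repeat. Those subjects stay in; the subset is those who had one procedure.
- *The listed rate will flatter the device against its own primary result.* That depends on how re-ablated subjects fare, as the last calculation shows.
- *The sponsor intends this figure to back the benefit listed in section 8.3, "Effective single treatment success rate".* That section speaks only of what the system may offer, without guarantee, and nothing links it to the analysis in 5.5. A reader might make the connection; the protocol does not.

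**Conclusion.** The point holds with limited weight. As an estimate of single-procedure effectiveness among all treated subjects, the rate in sections 5.5 and 6.7 is inflated by 1/(1 − r). This rests on reading those lines as they stand, with one-procedure subjects as the denominator. The direction is certain once anyone is re-ablated and at least one single-procedure subject succeeds. The size is not known: r is not in the protocol, and both the 54% base and the 5% to 20% range of r are hypothetical, giving about 3 to 13.5 points.

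Severity is low. It would be wrong to infer that study success is affected: the item is not tested and enters neither performance goal, nor the sample size, nor the interim stopping rules.

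**What to change.** In sections 5.5 and 6.7, define single-procedure chronic success over all treated subjects in the primary analysis cohort, counting any repeat ablation as failure for this descriptive analysis only. Report the number of subjects with a repeat beside the rate. The rate among one-procedure subjects may be kept as a second line if labelled as conditional on having had no repeat. The primary endpoint and its handling of repeats in the blanking period stay as they are.

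The cost is about one sentence in each section. No new data are needed, because section 7.3.3 (post-procedural care) already has the dates of repeat ablations recorded, and whether each was manual or robotic. The downside for the sponsor is a less favourable reported rate.
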